### 9.3.3. Events of Special Interest (ESIs)

The following events of special interest (ESIs) will be collected from the time of first administration of study product until Visit 5, Day 8 + 3 day:

- Pulmonary exacerbation, defined as:
  - Initiation of oral or IV antibiotics by the treating clinicians for respiratory symptoms, OR
    - Four or more of the following signs/symptoms:
      - Increase in both sputum quality and production
      - New or increased hemoptysis
      - Worsening cough
      - Increased shortness of breath
      - New onset malaise/fatigue/lethargy
      - Temperature  $> 38^{\circ}\text{C}$
      - Change in physical examination of the chest
      - Decrease in FEV1  $> 10\%$  from Baseline; and/or
      - Radiographic changes consistent with a pulmonary exacerbation.

Any ESI that meets the criteria of an SAE will be recorded and reported as an SAE instead of an ESI.

### 9.4. Deaths, Serious Adverse Events and Other Significant Adverse Events

Individual data listings of SAEs, ESIs, AEs leading to study product discontinuation, and deaths will be provided in [Table 56](#), [Table 57](#), [Table 58](#), and [Table 59](#), respectively.

Listings will include Subject ID, event description, date of onset, assessment of severity, relationship to study product and alternate etiology, date of resolution, seriousness, and outcome.

### 9.5. Pregnancies

Individual data listings of pregnancy reports will be provided if a pregnancy occurs post dosing:

- Maternal information will be presented in [Listing 27](#).
- Gravida and para information will be presented in [Listing 28](#).
- Live birth outcomes will be presented in [Listing 29](#), and still birth outcomes will be presented in [Listing 30](#).
- Spontaneous, elective, or therapeutic abortion outcomes will be presented in [Listing 31](#).

### 9.6. Clinical Laboratory Evaluations

After Protocol v5.0, Visit 6 (Study Day 12 + 7) was removed from the visit schedule for any subjects enrolling in Stage 2a or Stage 2b. Any laboratory summaries for Day 12 data will only show data from Stage 1 subjects. Any laboratory data collected during this visit for Stage 2a subjects who enrolled under the previous version of the Protocol will be included in lab listings only.

The distribution of laboratory results will be presented by severity, time point, and treatment group. Clinical chemistry parameters will be displayed beginning with [Table 63](#) and continuing through [Table 71](#), hematology parameters will be displayed beginning with [Table 80](#) and continuing through [Table 88](#), and liver function tests parameters will be displayed beginning with [Table 97](#) and continuing through [Table 104](#). Descriptive statistics, including mean, SD, median, minimum, maximum, and change from baseline by time point and treatment group will be presented beginning with [Table 72](#) and continuing through [Table 79](#) for clinical chemistry parameters, beginning with [Table 89](#) and continuing through [Table 96](#) for hematologic parameters, and beginning with [Table 105](#) and continuing through [Table 111](#) for liver function test parameters.

Graphical presentations of change from baseline at scheduled visits by treatment group and time point for each parameter as a series of box plots. Chemistry parameters will be presented beginning with [Figure 20](#) and continuing through [Figure 27](#). Hematology parameters will be presented beginning with [Figure 28](#) and continuing through [Figure 35](#). Liver function parameters will be presented beginning with [Figure 36](#) and continuing through [Figure 42](#).

Abnormal chemistry results will be presented in [Table 60](#), abnormal hematologic results will be presented in [Table 61](#), and abnormal liver function results will be presented in [Table 62](#).

All chemistry results will be presented in [Listing 18](#), all hematologic results will be presented in [Listing 19](#) and all liver function results will be presented in [Listing 20](#).

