2.3 Potential Risks and Benefits

2.3.1 Potential Risks

The scientific literature regarding the use of bacteriophage therapy for clinical use has not indicated any clear safety risks. As subjects will be receiving bacteriophage IV, there may be risks associated with this route of administration. Placement of a peripheral venous catheter can cause discomfort, minor bleeding, and infections from skin flora.

There have been several case reports and case series, as well as limited clinical trials investigating the safety of bacteriophage therapy. Although significant variability exists across published studies, there have not been SAEs related to bacteriophage therapy in the published literature. **Table 1** describes published studies on bacteriophage use in humans and includes reported adverse events (AEs). There are no consistent mild or moderate AEs across studies that have been associated with bacteriophage therapy.

From a theoretical point of view, the immediate lysis of bacteria following bacteriophage administration may result in skin flushing, hemodynamic changes in pulse and blood pressure, and respiratory difficulties.

From prior experiences with bacteriophage the following may occur, allergic reactions, temporary increases in liver enzymes, temporary shortness of breath or wheezing, temporary decrease in blood pressure, temporary feeling of being flushed or sweaty, development of fever, and temporary increase in heart rate.

A theoretical risk with bacteriophage therapy is the risk of transduction. This means the bacteriophage may serve as a vector to transfer DNA from one bacterium to another. The transferred DNA may include antibiotic resistance genes, as well as other clinically relevant genes. The likelihood of this occurring is unknown; however, experimental data from the current trial indicate this risk is very low. More specifically, whole genome sequencing analyses of paired *P. aeruginosa* isolates obtained from the sputum samples of 19 subjects pre and post bacteriophage or placebo treatment from Stage 2a were performed to assess whether there was any evidence of transduction by bacteriophage among subjects enrolled in the trial. The results indicate that there is no evidence of transduction by the bacteriophage within enrolled subjects.

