8.5 Procedures to be Followed in the Event of Abnormal Laboratory Test Values

Any Grade 2 or higher abnormal laboratory value will be reported as an AE, regardless of the relationship to the study product or clinical significance. Grade 1 laboratory abnormalities will be reported as AEs if assessed by the investigator as related to the study product. Laboratory abnormalities reported as AEs will be followed until the abnormality stabilizes, normalizes or returns to a baseline level, whichever comes first, at the discretion of the investigator.

In the approach to grading laboratory values, if the Lower Limit of Normal (LLN) entered at the site falls within CTCAE defined graded values, the CTCAE ranges will be used to grade an AE, rather than using local laboratory ranges for determining normal and abnormal laboratory values.

Intermittent abnormal laboratory values such as electrolyte abnormalities or blood glucose levels that are part of the same clinical diagnosis (e.g., uncontrolled diabetes) can be recorded once with the highest grade for each fluctuating AE (Grade 2 or higher for this trial), including the start and stop dates of the intermittent syndrome. If the event has a clear resolution for a duration of at least 48 hours and then recurs, it should be treated as a separate AE. An AE resolution is defined as return to pre-treatment status or baseline for duration of more than 48 hours.

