### 14.3.5 Displays of Laboratory Results

#### 14.3.5.1 Chemistry Results

**Table 63: Chemistry Laboratory Results by Parameter, Maximum Severity, Time Point, and Treatment Group – Any Chemistry Parameter**

[Implementation note: If no missing or outside normal range (ONR) results are reported, these columns will not be included, and corresponding footnotes should be removed. If parameter is not graded then only ‘Within Normal Range’, ‘Outside Normal Range’, and ‘Missing’ columns will be included.]

Treatment group order: All subjects,  $4 \times 10^7$  PFU Dose,  $4 \times 10^8$  PFU Dose,  $4 \times 10^9$  PFU Dose, Placebo.]

Time Point	Treatment Group	N	None		Outside Normal Range a		Mild/ Grade 1		Moderate/ Grade 2		Severe/ Grade 3		Missing	
			n	%	n	%	n	%	n	%	n	%	n	%
Stage 1														
Baseline	All Subjects (N=X)	x	x	xx	x	xx	x	xx	x	xx	x	xx	x	xx
	...													
	Placebo	x	x	xx	x	xx	x	xx	x	xx	x	xx	x	xx
Day 2	All Subjects (N=X)	x	x	xx	x	xx	x	xx	x	xx	x	xx	x	xx
	...													
Day 5	All Subjects (N=X)	x	x	xx	x	xx	x	xx	x	xx	x	xx	x	xx
	...													
Day 8	All Subjects (N=X)	x	x	xx	x	xx	x	xx	x	xx	x	xx	x	xx
	...													
Day 12 b	All Subjects (N=X)	x	x	xx	x	xx	x	xx	x	xx	x	xx	x	xx
	...													
Day 30	All Subjects (N=X)	x	x	xx	x	xx	x	xx	x	xx	x	xx	x	xx
	...													
Max Severity Post Baseline	All Subjects (N=X)	x	x	xx	x	xx	x	xx	x	xx	x	xx	x	xx
	...													

**Table 63: Chemistry Laboratory Results by Parameter, Maximum Severity, Time Point, and Treatment Group – Any Chemistry Parameter (continued)**

Time Point	Treatment Group	N	None		Outside Normal Range a		Mild/ Grade 1		Moderate/ Grade 2		Severe/ Grade 3		Missing	
			n	%	n	%	n	%	n	%	n	%	n	%
Stage 2a														
...														
Stage 2a and 2b														
...														

Notes: The “Max Post Baseline” rows indicate the maximum severity experienced by each subject at any time point post baseline, including unscheduled assessments.

N=Number of subjects in the Safety Population

aPost-dose measurements that were outside the normal range but did not meet the definition for an AE due to the value being less than or equal to the measurement at baseline will be categorized as “Outside Normal Range”

bOnly data from Stage 1 subjects will be summarized for this visit. Any Stage 2a subjects with Day 12 data will be included only in lab listings.

Tables with similar format:

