### 14.3.6 Displays of Vital Signs

**Table 112: Vital Signs by Assessment, Maximum Severity, Time Point, and Treatment Group – Any Assessment**

[Implementation note: Treatment group order: All subjects,  $4 \times 10^7$  PFU Dose,  $4 \times 10^8$  PFU Dose,  $4 \times 10^9$  PFU Dose, Placebo.]

Time Point	Treatment Group	N	None		Mild/ Grade 1		Moderate/ Grade 2		Severe/ Grade 3		Missing	
			n	%	n	%	n	%	n	%	n	%
Stage 1												
Baseline	All Subjects (N=X)	x	x	xx	x	xx	x	xx	x	xx	x	xx
	...											
	Placebo	x	xx	x	xx	x	xx	x	xx	x	xx	x
Day 2	All Subjects (N=X)	x	xx	x	xx	x	xx	x	xx	x	xx	x
	...											
Day 5	All Subjects (N=X)	x	xx	x	xx	x	xx	x	xx	x	xx	x
	...											
Day 8	All Subjects (N=X)	x	xx	x	xx	x	xx	x	xx	x	xx	x
	...											
Day 12 a	All Subjects (N=X)	x	xx	x	xx	x	xx	x	xx	x	xx	x
	...											
Day 30	4x10  PFU Dose (N=X)	x	xx	x	xx	x	xx	x	xx	x	xx	x
	...											
Max Severity Post Baseline	All Subjects (N=X)	x	xx	x	xx	x	xx	x	xx	x	xx	x
	...											
Stage 2a												
...												
Stage 2a and 2b												
...												

Notes: N=Number of subjects in the Safety Population.

n=Number of subjects in the Safety Population with non-missing vital sign values at the time point of interest.

aOnly data from Stage 1 subjects will be summarized for this visit. Any Stage 2a subjects with Day 12 data will be included only in lab listings.

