### 14.3.5 Displays of Laboratory Results

#### 14.3.5.1 Chemistry Results

**Figure 20: Chemistry Laboratory Results by Scheduled Visits: Mean Changes from Baseline by Laboratory Parameter, Treatment Group, and Time Point – Serum Creatinine**

[Implementation note: Correct units will be displayed for each parameter. Titles will have  $10^7$ , etc. displayed as superscript. ‘d12’ will be presented instead of ‘d11’ and only contain data from Stage 1 subjects.]

Figures with similar format:

**Figure 21:** Chemistry Laboratory Results by Scheduled Visits: Mean Changes from Baseline by Laboratory Parameter, Treatment Group, and Time Point – Blood Urea Nitrogen (BUN)

**Figure 22:** Chemistry Laboratory Results by Scheduled Visits: Mean Changes from Baseline by Laboratory Parameter, Treatment Group, and Time Point – Glucose

**Figure 23:** Chemistry Laboratory Results by Scheduled Visits: Mean Changes from Baseline by Laboratory Parameter, Treatment Group, and Time Point – Sodium

**Figure 24:** Chemistry Laboratory Results by Scheduled Visits: Mean Changes from Baseline by Laboratory Parameter, Treatment Group, and Time Point – Potassium

**Figure 25:** Chemistry Laboratory Results by Scheduled Visits: Mean Changes from Baseline by Laboratory Parameter, Treatment Group, and Time Point – Chloride

**Figure 26:** Chemistry Laboratory Results by Scheduled Visits: Mean Changes from Baseline by Laboratory Parameter, Treatment Group, and Time Point – Bicarbonate

**Figure 27:** Chemistry Laboratory Results by Scheduled Visits: Mean Changes from Baseline by Laboratory Parameter, Treatment Group, and Time Point – Calcium

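### SAP 9.6 sends Stage 2a Day 12 laboratory values to listings only; this conflicts with the shells' definition of maximum post-baseline severity and leaves observed data out of the by-dose Day 12 summaries

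*SAP*

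**What the plan says.** SAP 9.6 explains that, after Protocol v5.0, Visit 6 (Day 12 + 7) "was removed from the visit schedule for any subjects enrolling in Stage 2a or Stage 2b". Two consequences follow in the same paragraph. First: "Any laboratory summaries for Day 12 data will only show data from Stage 1 subjects". Second, Day 12 laboratory data "for Stage 2a subjects who enrolled under the previous version of the Protocol will be included in lab listings only".

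The shells repeat the rule. Footnote b on the Day 12 row of Tables 63, 80 and 97, and footnote a in the summary-statistics shells (Tables 72, 89 and 105), limit that row to Stage 1. The Figure 20 note says the Day 12 panel will be shown "and only contain data from Stage 1 subjects". The vital-sign shells (Tables 112 and 118) carry the same footnote: "Any Stage 2a subjects with Day 12 data will be included only in lab listings".

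The notes to Tables 63, 80 and 97 also define the Max Post Baseline rows as "the maximum severity experienced by each subject at any time point post baseline, including unscheduled assessments". They make no exception for Stage 2a Day 12 values.

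Protocol 10.5.10 promises laboratory values and changes from baseline by treatment arm at each assessment time point. Protocol 2.3.1 names "temporary increases in liver enzymes" among the effects that may occur.

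**The concern.** The two SAP rules cannot both be followed. A programmer who follows 9.6 leaves a scheduled Day 12 value out of a Stage 2a subject's maximum but counts an unscheduled value from the same week. One who follows the table notes counts both. The same data could give two different severity tables.

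The by-visit tables and box plots are not ambiguous: the Stage 2a Day 12 values are left out. The reason given, that the visit was later dropped, explains why there are fewer observations. It does not explain leaving out those that were made. Stage 2a is the only randomized, placebo-controlled stage with all three doses, so its laboratory tables are where a dose-related pattern in a named risk would be looked for. A Day 12 value of Grade 2 or higher would appear in the adverse event tables but perhaps not in the laboratory severity table for the same subject, and the two would then disagree.

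**Working it through.** The plan gives no figure to reproduce. The check is which outputs a Stage 2a Day 12 value reaches, and how far one value can move a table.

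**1. Tracing a Stage 2a Day 12 liver value**

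| Output | Does the value appear? |
|---|---|
| Day 12 row, Stage 2a block, Table 97 and its per-parameter versions | No (9.6, footnote b) |
| Change-from-baseline tables (Table 105 onward) | No (footnote a) |
| Box plots (Figure 36 onward, modelled on Figure 20) | No (Figure 20 note) |
| Max Severity Post Baseline row, Table 97 | No under 9.6; yes under the table's own note |
| Listing 20, and Table 62 if abnormal | Yes, with treatment group |
| AE tables, if Grade 2 or higher | Yes |

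The last row follows from Protocol 8.5: "Any Grade 2 or higher abnormal laboratory value will be reported as an AE, regardless of the relationship to the study product". If treatment-emergent, the event enters Table 44, the primary safety endpoint by dose. It also enters the Stage 2a and pooled AE tables by maximum severity (Tables 50 and 51). A Grade 1 value is an AE only if judged related, so an unrelated Grade 1 rise would appear in listings alone.

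**2. Vital signs**

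SAP 9.7 contains no Stage 1-only rule; the rule appears only in the footnotes to Tables 112 and 118. Those footnotes point to lab listings, but vital signs are in Listing 21. Table 112 has a maximum-severity row, but its notes do not define it.

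**3. Size**

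- Arm size in Stage 2a: 32 / 4 = 8.
- Largest share of a final arm that could have Day 12 labs: 8/20 = 40%, or 8/25 = 32%.
- Effect of one case seen only at Day 12 on the maximum-severity row, with exact Clopper-Pearson 95% intervals:

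| Arm size | Day 12 left out | Day 12 counted |
|---|---|---|
| 8 | 0% (0 to 36.9%) | 1/8 = 12.5% (0.3 to 52.7%) |
| 20 | 0% (0 to 16.8%) | 1/20 = 5% (0.1 to 24.9%) |
| 25 | 0% (0 to 13.7%) | 1/25 = 4% (0.1 to 20.4%) |

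The documents do not say how many Stage 2a subjects had the visit. The range is 0 to 32, at most 8 per arm.

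**4. How much a Day 12 draw adds (illustration, on assumptions)**

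A rise lasting d days is caught by a draw on day t if onset falls between t − d and t. Assume onset is uniform over Days 1 to 30 (length 29). The share caught is the length of the union of these intervals, cut off at Day 1, divided by 29.

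| Other draws | d | Without Day 12 | With Day 12 |
|---|---|---|---|
| Days 2, 5, 30 | 5 | 9/29 = 31% | 14/29 = 48% |
| Days 2, 5, 30 | 7 | 11/29 = 38% | 18/29 = 62% |
| Days 2, 5, 8, 30 | 5 | 12/29 = 41% | 16/29 = 55% |
| Days 2, 5, 8, 30 | 7 | 14/29 = 48% | 18/29 = 62% |

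If onset instead falls within Days 1 to 5 and the rise lasts 5 days, the nominal Day 5 draw catches every case and Day 12 adds nothing. The gain can therefore be zero.

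**The case against.** The sponsor can fairly answer that the SAP discloses the rule openly, that a visit dropped partway through Stage 2 makes an awkward by-visit row on a partial subset, and that nothing is lost from the report. Most of that stands. Grade 2 or higher values reach the by-dose AE tables, all laboratory results are in Listings 18 to 20, and abnormal ones are also in Tables 60 to 62. SAP 9.7 puts all vital signs in Listing 21, so the vital-sign footnote is a slip in wording.

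Two stronger readings are tempting, and the documents support neither.

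- A reader might infer that a Day 12 rise is missing from the maximum-severity rows. The notes to Tables 63, 80 and 97 point the other way. Footnote b is attached to the Day 12 row and speaks of that visit. Omission from the maximum is one of two possible readings.
- A reader might infer from the current schedule that Day 12 held the only scheduled labs between Visit 4 and Visit 7. The affected subjects enrolled under an earlier protocol that is not supplied. SAP 4.5 lists Day 8 among the laboratory days and the laboratory shells carry Day 8 rows, although the current protocol schedules no Day 8 labs. Whether these subjects had them is unknown.

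The objection does not dispose of the conflict between 9.6 and the table notes, or of the omission of observed values from the Stage 2a Day 12 summaries despite Protocol 10.5.10.

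**Conclusion.** The point holds as an unresolved conflict in the SAP, together with a stated rule that keeps observed, randomized safety data out of the Stage 2a Day 12 rows, change-from-baseline tables and box plots. It concerns the laboratory and vital-sign summaries only. The primary safety endpoint and the listings are not affected.

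One case seen only at Day 12 moves a Stage 2a arm by 12.5 percentage points and a final arm of 20 to 25 by 4 to 5 points. These figures assume that such a case exists; the number of subjects with Day 12 data could be zero. SAP 9.6 speaks only of laboratory data from this visit. That Stage 2a subjects also had Day 12 vital signs is inferred from the footnotes to Tables 112 and 118. The change is worth making because it is cheap and the table notes already imply it.

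**What to change.** 1. In SAP 9.6 and the Day 12 footnotes, state that all Stage 2a Day 12 values count in Max Severity Post Baseline, as the notes to Tables 63, 80 and 97 already say. Add the same definition to Table 112.
2. Report by arm how many Stage 2a subjects had the Day 12 visit, preferably as a Day 12 row with its own n in the Stage 2a block only.
3. Correct the footnotes to Tables 112 and 118 to refer to Listing 21.
4. Correct the Table 62 implementation note, which asks for urinalysis results where it should ask for liver function results. The Table 60 note has a similar slip: it asks for hematology results in the chemistry listing.

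The cost is SAP wording and minor programming, with no new data. There is one small downside. In the pooled Stage 2a and 2b block, some Stage 2a subjects contribute one more visit to the maximum. The selected dose and placebo share the same planned mix of stages, but the two dropped doses consist of Stage 2a subjects only. A footnote should say so.

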## 9.7. Vital Signs and Physical Evaluations

Descriptive statistics and change from baseline will be summarized for the following vital signs: systolic and diastolic blood pressure (BP) in millimeters of mercury (mmHg), heart rate (beats per minute [BPM]), respiratory rate, and body temperature in degrees Celsius (°C; oral measurement). Vital signs will be collected at baseline, Days 2, 5, 12, 30, and ET or unscheduled study visits.

The proportion of subjects with mild, moderate, or severe vital sign results will be presented by parameter, treatment group, and time point beginning with [Table 112](#) and continuing through [Table 117](#). Vital sign measurement values and change from baseline will be presented by parameter, treatment group, and time point beginning with [Table 118](#) and continuing through [Table 122](#). All vital sign results will be presented in [Listing 21](#). Graphical presentation of change from baseline at scheduled visits by treatment group and time point will be presented for each vital sign parameter beginning with [Figure 43](#) and continuing through [Figure 47](#).

Symptom directed physical examinations will be performed at baseline, Days 2, 5, 12, 30, and ET or unscheduled study visits. A listing of physical exam findings will be presented in [Listing 22](#). A listing of review of systems findings will be presented in [Listing 23](#).

Spirometry will occur prior to required sputum collections. Spirometry values will be presented in [Listing 24](#).

## **10. PHARMACOKINETICS**

Analysis of PK endpoints will be provided in separate analysis plan document.

## **11. IMMUNOGENICITY**

Not applicable.

## **12. OTHER ANALYSES**

Not applicable.

### 13. REPORTING CONVENTIONS

P-values  $\geq 0.001$  and  $\leq 0.999$  will be reported to 3 decimal places; p-values less than 0.001 will be reported as “ $< 0.001$ .” The mean, standard deviation, and other statistics will be reported to 1 decimal place greater than the original data. The minimum and maximum will use the same number of decimal places as the original data. Proportions will be reported to the nearest hundredth; values greater than zero but  $< 0.01$  will be presented as “ $< 0.01$ ”. Percentages will be reported to the nearest whole number; values greater than zero but  $< 1\%$  will be presented as “ $< 1\%$ ”; values greater than 99% but less than 100% will be reported as “ $> 99\%$ ”. Estimated parameters, not on the same scale as raw observations (e.g., regression coefficients) will be reported to 3 significant figures.

